5.3.6 Treatment Period - Telephone Contact (Both Phases)

Cycle 1, Day 22 (± 2 days)

Cycle 2 - Days 8, 15, and 22 (± 2 days)

Cycles 3+ - Day 15 (± 2 days)

- Adverse event assessment using NCI CTCAE, Version 5.0
- Concomitant medications

5.3.7 Treatment Period Office Visit – Cycle 2+, Day 1

- Weight
- Physical examination
- Vital Signs
- Resting O₂ Saturation
- ECOG Performance Status assessment
- Pregnancy test in women of childbearing potential
- Complete blood count with 5-part differential
- Serum chemistry, including KL-6 and C-reactive protein
- Imaging Session
 - Tumor assessment (to be performed at approximately 4 weeks (Cycle 2, Day 1 [up to Cycle 2, Day 10]), 8 weeks (Cycle 3, Day 1 [up to Cycle 3, Day 10, with at least 28 days from previous tumor assessment]), and approximately every 8 weeks [± 10 days]) thereafter)
 - Whole blood samples (20 mL) on Cycle 2, Day 1, Cycle 3, Day 1, and then every 8 weeks
 - Pulmonary Function Assessment
 - 12-lead ECG prior to that day's patient dose and 1 and 2 hours postdose (**Cycle 2 only**)

- Pharmacokinetic blood sampling (**4 mL**):
 - **Phase 2:** Predose and 1 and 2 hours postdose (± 15 minutes) samples drawn on Cycle 2, Day 1 only and predose on Cycle 3, Day 1 and then every 8 weeks.
- Collect and dispense pozotinib
- Dispense supportive care medications as needed
- Adverse event assessment using NCI CTCAE, Version 5.0
- Concomitant medications
- Patient Diary collected and dispensed

5.3.8 Safety Follow-up/End-of-Study Visit (35 [± 5] Days after Last Dose of Study Treatment)

The **Safety Follow-up Visit** is required 35 (± 5) days after the last dose of pozotinib is administered. The following assessments are to be performed at this visit:

- Weight
- Physical examination
- Vital signs
- Pulmonary Function Assessment and Resting O₂ Saturation
- ECOG Performance Status assessment
- Pregnancy test in women of childbearing potential
- Tumor assessment (unless the patient has documented disease progression or has undergone a tumor assessment within the previous 8 weeks)
- Complete blood count with 5-part differential
- Serum chemistry, including KL-6 and C-reactive protein
- 12-lead ECG
- Newly biopsied tumor tissue taken from patients who progress (optional, but highly encouraged) (**Phase 2 only**)
- Whole blood samples for plasma ctDNA analysis if the patient progresses (optional) (**Phase 2 only**)
- Adverse event assessment using NCI CTCAE, Version 5.0
- Concomitant medications
- Patient diary collected

5.3.9 Long-Term Follow-up – Every 3 Months

- After study drug discontinuation, patients will be contacted every 3 months, for up to 2 years after patient's first dose of pozotinib, for survival assessment.

5.4 Description of Study Assessment Parameters

5.4.1 Relevant Medical History

At Screening, the patient's relevant medical history, including type of cancer, HER2 and EGFR status (optional in Phase 1), history of tobacco use, previous therapies, and current medications will be collected.

5.4.2 Physical Examination

A complete physical examination, including a description of external signs of the neoplastic disease and co-morbidities, will be performed at Screening and Day 1 of each cycle, and at the Safety Follow-up Visit. Symptom-directed examinations are required at other visits. In addition, physical examination will be done on days 7 and 14 of Cycle 1 while Phase 1 patients are in the hospital, and Cycle 1, Days 8 and 15 for Phase 2 patients. Physical examinations are to be completed by a physician or other health professional licensed to perform such examinations. Findings will be documented in the patient's medical record and on the appropriate CRF pages. Any abnormalities are to be recorded on the AE CRF.

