7.2 Adverse Events

An AE is defined as any untoward medical occurrence in a patient or clinical investigation patient, temporally associated with the use of a medicinal product, whether or not considered related to the medicinal product. Therefore, an AE can be any unfavorable and unintended sign (including an abnormal laboratory finding), symptom, or disease (new or exacerbated) temporally associated with the use of a medicinal product. A treatment-emergent AE (TEAE) is any AE that occurs from the first dose of study treatment until 35 (± 5) days after the last dose of study treatment.

The study will record all AEs according to the information in [Section 7.3](#).

Examples of AEs **include**:

- Exacerbation of a chronic or intermittent pre-existing condition including either an increase in frequency and/or intensity of the condition.
- New conditions detected or diagnosed after investigational product administration.
- Signs, symptoms, or the clinical sequelae of a suspected drug interaction.
- Signs, symptoms, or the clinical sequelae of a suspected overdose of either investigational product or a concurrent medication.
- AEs may include pre-treatment or post-treatment events that occur as a result of protocol-mandated procedures, ie, invasive procedures.

Abnormal laboratory results are to be recorded as AEs, if any of the following conditions are met:

- The abnormal laboratory value leads to a therapeutic intervention.

- The abnormal laboratory value is considered to be clinically significant by the Investigator.
- The abnormal laboratory value is predefined as an AE in the protocol or in another document communicated to the Investigator by Spectrum or designee.

Examples of events that **do not** constitute AEs include:

- Medical or surgical procedures (eg, endoscopy, appendectomy); the condition that leads to the procedure is an AE.
- Situations where an untoward medical occurrence does not occur (eg, social and/or convenience admission to a hospital).
- Anticipated day-to-day fluctuations of pre-existing disease(s) or condition(s) present or detected at the start of the study that do not worsen.
- Planned and prescheduled hospitalizations and procedures.
- Progressive disease and death due to disease progression.

The adverse events of special interest identified with pozotinib treatment in this study include diarrhea, skin rash, oral cavity mucositis/stomatitis, fatigue, and vomiting/nausea.

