7.3.1 Recording of Adverse Events

All AEs that occur from the first dose of study treatment through 35 (± 5) days after the last dose of study treatment is administered are to be recorded on the AE CRF. From the time the study Informed Consent is signed through the first dose of study drug administration, all SAEs are to be recorded. In addition, SAEs that occur after 35 (± 5) days after the last dose of study treatment where a causal relationship with the study drug is suspected will also be recorded on the AE CRF.

The resolution of all AEs must be routinely recorded and be reconciled at the end of the study. The following conventions will be followed when patient completes or discontinues from the study:

- If a patient dies, the date of death should be the date of AE stop for all ongoing AEs at the time of death.
- The outcome of the AE is to be followed for 35 (± 5) days from the date of discontinuation or until the AE has returned to Grade ≤ 1 . The status of the AE and the date of last contact with the patient will be captured. If the AE has not returned to Grade ≤ 1 by the end of the study, the AE stop date should be left as ongoing.

All AEs will be classified by CTCAE Grade ([Section 7.3.2](#)), relationship to study drug ([Section 7.5](#)), and as serious or nonserious ([Section 7.7](#)) by the Investigator.

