8.6.1 Safety and Adverse Events

Safety will be assessed by reported/elicited AEs, laboratory assessments including hematology and chemistry, vital signs, physical examination, and neurological examination. The assessment of treatment-emergent AEs (TEAEs) includes SAEs, AEs leading to study drug discontinuation, and AEs related to the study drug.

The overall incidence of treatment-emergent AEs (TEAE) (ie, AEs occurring from the time the first dose of the study drug until 35 (\pm 5) days after the last dose) and the proportion of patients who discontinue because of a TEAE are the primary safety outcome measures. The number and percent of patients with new-onset TEAEs will be summarized by the MedDRA system-organ-class (SOC) level and Preferred Term for all treated patients, for each cohort. The summary of TEAEs will be presented in the following categories:

- Number and percentage of patients with any TEAEs by SOC and Preferred Term.
- Number and percentage of patients with any SAEs by SOC and Preferred Term.
- Number and percentage of patients with related TEAEs by SOC and Preferred Term.
- Number and percentage of patients with TEAEs causing discontinuation of the study by Body System and Preferred Term.

In addition, the number and percent of patients with TEAEs by grade will be summarized. Serious adverse events reported prior to treatment but after IC will be provided in a listing.

The number of completed cycles will also be summarized and analyzed descriptively.

All laboratory abnormalities will be classified according to CTCAE version 5.0 and summarized by toxicity grade.

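### Section 5.4.2 sends every physical-examination abnormality to the AE form, which conflicts with the AE definition in 7.2 for unchanged baseline signs and with the recording window in 7.3.1 for Screening findings

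*Combined protocol and SAP*

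**What the plan says.** Section 5.4.2 (Physical Examination) requires a complete examination at Screening, on Day 1 of each cycle and at the Safety Follow-up Visit, "including a description of external signs of the neoplastic disease and co-morbidities". Findings go to the medical record and the relevant CRF pages. The closing sentence then adds: "Any abnormalities are to be recorded on the AE CRF".

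Section 7.2 (Adverse Events) limits the disease part of the AE definition to disease that is new or has become worse. Its list of what is not an AE includes "Anticipated day-to-day fluctuations of pre-existing disease(s) or condition(s) present or detected at the start of the study that do not worsen" and "Progressive disease and death due to disease progression". Section 7.7.2 repeats both exclusions for SAEs. For laboratory values, 7.2 gives conditions for AE status, one of which is that "The abnormal laboratory value is considered to be clinically significant by the Investigator". It gives no such filter for examination findings.

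Section 7.3.1 sets the recording window: "All AEs that occur from the first dose of study treatment through 35 (± 5) days after the last dose" go on the AE form, and between consent and first dose only SAEs are recorded. Footnote t of the Phase 1 schedule and footnote v of the Phase 2 schedule say the same for Screening.

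A TEAE is defined in 7.2 by timing only, as "any AE that occurs from the first dose of study treatment until 35" (± 5) days after the last dose. In 8.6.1, "The number and percent of patients with new-onset TEAEs will be summarized" by System Organ Class (SOC) and Preferred Term for each cohort. New-onset is not defined.

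**The concern.** Every patient enrolled has locally advanced or metastatic NSCLC, so abnormal findings at baseline are to be expected. For an unchanged tumor sign or comorbidity, an examiner cannot follow both 5.4.2 and 7.2: the first requires an AE entry and the second says there is no AE. Neither section says which takes precedence.

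At stake are the SOC and Preferred Term tables. The trial has no untreated control group against which to judge the disease background. Phase 2 cohorts have 20 patients, and about 76 patients are spread over about 20 centers. If sites resolve the conflict differently, term-level rates will partly reflect recording practice. Respiratory terms deserve most care, because auscultation is part of the monitoring for interstitial lung disease (ILD) in 5.4.4.

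**Working it through.** The documents give no count of examination abnormalities, so there is no plan figure to reproduce. The check takes each kind of finding and applies the rules to it.

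1. **Non-serious abnormality at the Screening examination.** Under 5.4.2 it goes on the AE form. Under 7.3.1 and footnotes t and v it does not, since only SAEs are recorded before first dose. The rules conflict. If the finding is dated correctly it precedes the first dose and is not a TEAE, so the damage is to the AE data set and not to the TEAE tables.

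2. **Unchanged baseline sign first written down on or after Cycle 1 Day 1.** Under 5.4.2 it goes on the AE form. Under 7.2 it is not an AE. The rules conflict. Another examination is scheduled on Cycle 1 Day 1 and at later visits, so there is ample occasion for this. Once entered with an on-treatment date, the finding meets the timing definition of a TEAE. The undefined new-onset wording in 8.6.1 does not clearly remove it, and the first summary listed there covers any TEAE by SOC and Preferred Term without that qualifier.

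3. **Baseline sign that worsens after first dose.** 5.4.2 and 7.2 both lead to an AE entry. No conflict.

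4. **New sign after first dose.** 5.4.2 leads to an AE entry. Section 7.2 counts unfavorable signs and conditions first detected after dosing as AEs, whether or not they are related to the drug. No clear conflict.

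The contradiction is therefore confined to cases 1 and 2, and only case 2 reaches the TEAE tables.

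Scale, from the planned numbers:
- One patient wrongly counted under a term in a Phase 2 cohort: 1/20 = 5 percentage points on that term.
- Average patients per center: 76/20 = 3.8, so differences in site practice have little chance to average out.
- Any-TEAE incidence was 95-100% in the earlier study groups of Table 1, so extra entries can hardly move it.

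The number of patients in case 2 is unknown. The 5 points are a per-patient sensitivity, not an estimate of the effect.

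**The case against.** The best defense is that the sections can be read together. Section 7.2 defines an AE, 7.3.1 says where AEs are recorded, and 5.4.2 only tells the examiner where abnormalities that are AEs should go. Baseline signs have a home on other CRF pages, mentioned just before the disputed sentence. Screening is limited to SAEs by the footnotes, TEAEs start at first dose, and 8.6.1 speaks of new-onset events. Section 7.3 also refers sites to CRF Completion Guidelines, which are not among the documents and may settle the matter.

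This shows what was probably intended. It does not remove the conflict: the last sentence of 5.4.2 is a direct instruction without a qualifier, it adds the AE form to the other pages, new-onset is undefined, and a guideline should not have to overrule the protocol.

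The defense is stronger on consequences. Every AE gets a causality rating (7.5), 8.6.1 tabulates related TEAEs separately, and dose-limiting toxicities must be treatment-related. The two primary safety measures are overall TEAE incidence, which is near its ceiling, and discontinuation because of a TEAE. Section 4.3 lists progression and AEs as separate reasons for withdrawal. All of this stands and limits the harm.

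A reader might go further and infer that every new tumor sign found on treatment is a non-AE that 5.4.2 wrongly turns into a TEAE. The text does not support that. Section 7.2 excludes progressive disease as such, not each sign that may accompany it, and its general definition takes in new unfavorable signs. Nor does 7.3.1 exclude pre-existing conditions or progression; it sets only the recording window.

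**Conclusion.** The conflict is real and narrow. Section 5.4.2, read literally, contradicts 7.3.1 and the footnotes for non-serious Screening findings, and contradicts 7.2 for unchanged baseline signs first recorded on or after Cycle 1 Day 1. The second group can enter the SOC and Preferred Term tables as TEAEs. This assumes that some sites follow the sentence as written and that the unseen CRF guidelines do not already correct it.

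The size cannot be derived from the documents. One might try to size the effect from the earlier NSCLC study, where 72.5% of patients are said to have left for progression or lack of efficacy: 0.725 × 20 = 14.5 per cohort, and if 20% to 40% of those had an examination sign, 2.9 to 5.8 patients, or about 15% to 29% of 20. That figure should not be used. The 20-40% share has no source in the documents. The population differed (acquired resistance to first-generation EGFR TKIs, not screened for exon 20 mutations). The percentage is printed beside 29/39, which is 74.4%. Above all, the calculation counts signs of progression, which are arguably AEs under 7.2 anyway.

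Overall TEAE incidence, the related-TEAE tables and the efficacy analyses are little affected. This is a data-recording rule that should be corrected, with modest impact.

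**What to change.** Replace the last sentence of 5.4.2 with: *Abnormalities present before the first dose are recorded as medical history or on the physical-examination CRF page (and as an SAE if serious). After the first dose, new or worsened abnormalities that meet the adverse event definition in Section 7.2 are recorded on the AE CRF.*

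In 8.6.1, define new-onset as new or worsened relative to baseline, and apply that definition to all the TEAE summaries listed there.

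The change should not redirect signs attributed to progression to the tumor assessment. Section 5.4.6 describes an imaging-based RECIST assessment with no stated place for examination signs, and moving respiratory signs off the AE form could hide possible ILD. New respiratory signs should stay on the AE form under 7.2.

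The cost is a few sentences in an amendment and a matching line in the CRF guidelines. No new data or procedures are needed.

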5.4.3 Vital Signs

Vital signs, to include temperature, blood pressure, heart rate, and respiratory rate, are to be recorded at Screening and Day 1 of each cycle and at the Safety Follow-up Visit. In addition, vital signs will be taken on days 7 and 14 of Cycle 1 while Phase 1 patients are in the hospital, and Cycle 1, Days 8 and 15 for Phase 2 patients the patient is in the hospital. Heart rate and blood pressure will be recorded before pozotinib administration.

5.4.4 Pulmonary Function and Resting Oxygen Saturation

During the Screening Period the patient will be assessed for cofactors that may predispose to the development of pneumonitis including previous pneumonitis including radiation pneumonitis, radiation therapy to the lung fields, prior extensive chemotherapy, prior checkpoint inhibitor therapy, and connective tissue disease (rheumatoid arthritis, scleroderma, LES).

In Phase 1, resting O₂ saturation will be assessed at Screening, daily for the first 2 weeks of Cycle 1, while the patient is hospitalized, on Day 1 of all subsequent cycles, and at the Safety Follow-up Visit. In Phase 2, resting O₂ saturation will be assessed at Screening, Cycle 1, Days 1, 8, and 15, on Day 1 of all subsequent cycles, and at the Safety Follow-up Visit.

In both phases, screening and monitoring for evidence of interstitial lung disease (ILD) by verbal discussion with the patient regarding breathing signs and symptoms, physical examination including auscultation, and pulmonary function tests (spirometry) will be performed.

- In Phase 1, pulmonary function will be assessed at Screening, on Day 1 of Cycles 1-3, every 8 weeks thereafter, and at the Safety Follow-up Visit. In addition, evidence of ILD will be assessed on Cycle 1, Days 7 and 14 while the patient is in the hospital.
- In Phase 2, pulmonary function will be assessed at Screening, on Day 1 of Cycles 1-3, every 8 weeks thereafter, and at the Safety Follow-up Visit. In addition, evidence of ILD will be assessed on Cycle 1, Days 8 and 15.

5.4.5 ECOG Performance Status

Patients' Performance Status will be evaluated using criteria as developed by the Eastern Cooperative Oncology Group ([Appendix 3](#)) at Screening and Day 1 of each cycle and at the Safety Follow-up Visit. In addition, in Phase 1, ECOG will also be evaluated on days 7 and 14 of Cycle 1 while the patient is in the hospital and in Phase 2 will be assessed on Cycle 1, Days 8 and 15.

5.4.6 Tumor Assessment

Results of standard-of-care tests or examinations performed within 28 days prior to Cycle 1, Day 1 may be used for the Screening/Baseline tumor assessment. Tumor assessments must be performed using computed tomography (CT), positron emission tomography (PET)/CT, or magnetic resonance imaging (MRI). The image will be reviewed by a local radiologist as the Baseline image for response assessment and per the Investigator's standard of care.

For patients with known brain metastases, a Baseline brain MRI scan (within 28 weeks prior to Cycle 1, Day 1) will also be performed to assess the status of brain metastases if present.

Tumor assessments will also be performed at 4 weeks (Cycle 2, Day 1 [up to Cycle 2, Day 10]), 8 weeks (Cycle 3, Day 1 [up to Cycle 3, Day 10, with at least 28 days from previous tumor assessment]), and then every 8 weeks (\pm 10 days) for up to 24 months or until disease progression, death, intolerable adverse events (AEs), or other protocol-specified reasons for patient withdrawal or for a maximum of 24 months.

Tumor assessment will be performed at the Safety Follow up Visit unless the patient has documented disease progression or has undergone a tumor assessment within the previous 8 weeks.

Each subsequent tumor assessment must use the same baseline radiographic technique, either CT, PET/CT, or MRI. Tumor assessments will be made according to RECIST criteria, Version 1.1 [\[22\]](#) using appropriate radiographic imaging or other techniques. For radiographic assessment, CT, PET/CT, or MRI must be performed at every assessment. Patient enrollment and clinical decisions will be based on local review.

Measurable and non-measurable lesions that will not be followed by radiographic methods should be documented appropriately.

